Predictability of OSA with a Subjective Screening Scale

Predictive Value of OSA Based on the Evaluation of the Subjective Feeling of the Air Flow Through Airways, a Randomized Controlled Study

About the study protocol:

The oropharynx, due to its specific layout in humans, is unstable under the effect of inspiratory depression during ventilation. Continuous control of the oropharyngeal lumen is necessary to ensure optimal ventilation.

The combined role of all the pharyngeal dilator muscles and the muscles constituting the pharyngeal groove is essential for maintaining the patency of the pharyngeal upper airway. The action of these muscles allows for the postural adjustment of the pharyngeal cavities and the rigidity of the entire pharyngeal muscular groove.

The permeability of the upper airways is therefore largely dependent on optimal tone of the muscles constituting the walls of the upper airways. The management of the tone of these muscles is possible thanks to the numerous mechanosensory receptors present in the upper airways. There are many of them, among which some are sensitive to changes in shape, the passage of air, variations in temperature, pressure, etc. The opening reflex of the upper airways depends on the integrity and quality of these receptors. Several known factors can lead to an alteration of these receptors: vibrations of the soft palate, edema, inflammation, hypoxia, GERD, drying of the mucous membranes, postnasal drip, etc.

In sleep disorders, the excitability threshold of these receptors can vary depending on the extent of VAS resistance (SRAVAS), or even collapse (OSA). It is possible that the sensitivity of these receptors is exacerbated in cases of SRAVAS and mild OSA and reduced or even inhibited in severe forms of OSA.

Numerous parietal factors modify the volume and permeability of the pharynx (pharyngeal lumen) and act through different mechanisms:

- Modification of the pharyngeal lumen in the transverse and sagittal dimensions
- Modification of transmural parietal tension (longitudinal tension) and therefore of the compliance of the pharyngeal wall by the passive and active tension of the pharyngeal muscles (tonic, phasic)

Considering the permeability of the pharynx, we can identify biomechanical parameters that increase resistance to the passage of air in the upper airways (aggravating parameters) and others that decrease resistance (facilitating parameters).

Aggravating factors:

- Supine position

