- Altered state of consciousness (first sleep stage)
- Mouth breathing and loss of lingual-palatal and labial-labial contact
- Passive craniocervical flexion

Facilitating parameters:

- Cephalocervical extension
- Mandibular advancement
- Tongue protraction
- Efficient nasal ventilation

These considerations allow us to establish an examination protocol to attempt to answer the following questions:

- Can the subject consciously perceive variations in airflow/or intraluminal pressure in the upper airways caused by the various aggravating and facilitating parameters?
- Can the sensations of ventilatory flow/intraluminal pressure felt by the subject constitute a complementary tool for screening for obstructive sleep disorders?

The goal of the clinical examination is to cause instability of the oropharyngeal mechanics. This instability can cause a modification of the pharyngeal lumen and a modification of the resistance of the VAS to the pressure linked to the ventilatory flow. These will lead to a modification of the inspiratory pressure gradient and stimulate the mechanoreceptors located in the VAS. The responses to a questionnaire by subjects who present sleep disorders exposed to these variations in resistance (aggravating or facilitating) on their subjective feeling allows the establishment of a perception scale which, compared to a control group without sleep disorders, will determine if the sensitivity of the inputs is comparable between the groups and if a tool for screening sensory inputs is possible.

Protocol:

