The questionnaires to assess patients' pharyngeal ventilatory perceptual potential/the quality of spontaneous nasopharyngeal perception during ventilation are administered when patients come to the consultation to request the results of the pharyngeal ventilatory perceptual analysis. The examiners are blinded, unaware of the results. Patients are randomly assigned according to their order of arrival. The first questionnaire consists of 7 items selected to aggravate or facilitate upper airways permeability (supine position, modified state of consciousness with muscle relaxation, tongue posture, cephalic flexion, cephalic extension, mandibular protraction, nostrils aperture). This first questionnaire try to evaluate if all subjects are able to feel aggravating or facilitating factors by on/off answers. The second questionnaire consists of 18 items related to upper airway collapsibility. Each item concerns the aggravating or facilitating factors perceived by the patient or the therapist with clinical maneuvers, factors known to be unfavourable to the permeability of the upper airways (snoring, oral ventilation, tonsils, dento-skeletal class, etc.), as well as two questionnaires used in the sleep laboratory of the André Renard clinic (Epworth Sleepiness Scale and FFF questionnaire).

[figure not shown]
For each of these items, the patient's or practitioner's response will be noted.

Performing the examination:

- Sensory-motor awareness of nasal and pharyngeal breathing (patient in a seated position): explain to the patient what to observe and feel and where (soft palate, tonsils, vibration during snoring, etc.)
- Read the questionnaire to the patient: it must be understood
- Ask the patient to answer each item and record the response.

The examination lasts approximately 20 minutes.

This examination requires patient involvement but carries no risks or side effects.

STATISTICAL ANALYSIS PLAN

(translation of the Statistical analysis report download in SAP section from an independent Biostatistician: [name], MyStat.be)

Software used for analysis: R version 4.4.1(R Core Team (2024). R: A language and environment for statistical computing. R Foundation for Statistical Computing, Vienna, Austria. URL <https://www.R-project.org/>) and Microsoft Excel for manipulating and preparing the data tables. data files used and appended: d1_final.csv, d2_final.csv

1 - d1_final.csv: sensitivity parameters taken from 112 patients

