2 - d2_final.csv: parameters taken from 101 patients (excluding CHR patients considered normal after polysomnography)

Discrete variables for classification into groups :

- STATUS3: 2 categories: healthy patients (= non-CHR control patients and normal CHR patients) and pathological patients (= CHR patients affected to varying degrees)
- STATUS4: 4 categories: control patients (= non CHR), normal patients (= CHR N), mild symptom patients (= CHR SL), moderate symptom patients (= CHR SM) and severe symptom patients (= CHR SS).

A. Descriptive statistics (based on file n°1 - sensitivity)

B. Descriptive statistics (based on file n° 2 - predictive score)

C. Normality tests for intermediate and final scores

- Parameter ST1 (SubTotal1) = aggravating parameters

Shapiro-Wilk normality test

- Parameter ST2 (SubTotal2) = facilitating parameters

Shapiro-Wilk normality test

- Parameter ST1+ST2 (SubTotal1+ SubTotal2) = subjective sensitivity of patients

Shapiro-Wilk normality test

- Parameter ISF (Intermediate Final Score) = subjective sensitivity of patients and practitioner

Shapiro-Wilk normality test

- Parameter TFS (Total Final Score) = subjective sensitivity of patients and practitioner + valuable factors

Shapiro-Wilk normality test

D. Spearman correlation tests between final scores and certain variables

E. Non-parametric tests on patient sensitivity :

Given the non-normal distribution of the various variables other than IFS and TFS, non-parametric tests (based on the median of the data) were applied to analyse the differences between the groups (according to the STATUS3 and STATUS4 classification criteria). To analyse any differences in sensitivity between patient groups, Kruskal-Wallis tests were applied. In this type of analysis, having a p-value greater than 1% and ideally greater than 5% would indicate the absence of differences between groups.

Then, to see if the median of a particular group is different from 0 (= no sensitivity: not feeling the differences in airflow induced by the different tests given by the operator), Wilcoxon tests were performed on each group of data. If the p-value is small (less than 5%, ideally less than 1%), the null hypothesis that the score is identical to 0 is rejected. In this case, it means that the patients in the test group feel the differences in airflow depending on their position. This is the case for all the patient groups tested on ST1, ST2 and ST1+ST2.

[figure not shown]

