F. Parametric tests on the prediction of patients' pathological status (SFI and SFT scores):

For these analyses, as the IFS and TFS scores follow a normal distribution, ANOVAs (analyses of variance) were performed. For discrete variables with more than 2 levels of value (STATUS4), a post-hoc 2-to-2 comparison analysis was performed (Tukey) to see which level of the variable differed from one another. Significant values are highlighted in bold red.

[figure not shown]
G. Determination of cut-off values for IFS and TFS:

[figure not shown]
The Cutoff_final txt file includes the various sensitivity and specificity calculations as well as the Youden index in order to determine the best cut-off value (largest Youden). The ROC curves allow the values in the file to be appreciated graphically.

Upper rhino-oro-pharyngeal airway permeability - Subjective neuro-sensory evaluation

Assessment of oro-pharyngeal sensitivity				
Date :	Name:			age:
Tests	Items			Score 1 0
	Aggravation or facilitation felt = 1 No aggravation or no facilitation felt = 0			
Aggravation maneuver	1	Supine position		
Aggravation maneuver	2	Modified state of consciousness (overall relaxation)		
Aggravation maneuver	3	Cephalic Flexion		
Aggravation or Facilitation maneuver	4	Upper-anterior tongue to lower tongue (= aggravation) or lower tongue to upper-anterior tongue (= facilitation)		
Facilitation maneuver	5	Cephalic Extension		
Facilitation maneuver	6	Mandibular protrusion		
Facilitation maneuver	7	Nostrils aperture		
Total Score				... / 7
Comments :				
www.osteovox.be				

Upper rhino-oro-pharyngeal airway permeability - Subjective neuro-sensory evaluation						
Date :	Name :			age: IMC:		
Tests	Items			Scores		
	0	0,5	1	2		
Aggravation maneuver	1	Supine position: aggravation=1 / no aggravation= 0				
Aggravation maneuver	2	Modified state of consciousness (overall relaxation) aggravation=1 / no aggravation= 0				

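### The score comparisons in SAP sections F and G are between non-randomised groups that differ in sex, BMI and age, and no described analysis shows whether the score adds to these

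*Combined protocol and SAP*

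**What the plan says.** The title ends "Through Airways, a Randomized Controlled Study", and the Protocol section states: "Patients are randomly assigned according to their order of arrival". It does not say to what they are assigned.

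The SAP defines the groups that are compared. STATUS3 separates "healthy patients (= non-CHR control patients and normal CHR patients) and pathological patients (= CHR patients affected to varying degrees"; STATUS4 splits the same patients by source and severity. The second data file holds "parameters taken from 101 patients (excluding CHR patients considered normal after polysomnography", and heading B ties that file to the predictive score.

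Section F says that "as the IFS and TFS scores follow a normal distribution, ANOVAs (analyses of variance) were performed", with Tukey comparisons for STATUS4. Section G uses sensitivity, specificity, the Youden index and ROC curves to choose cut-offs. Neither names a covariate, matching, stratification or a model comparison. Section D lists "Spearman correlation tests between final scores and certain variables" without naming the variables.

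Among its study questions, the protocol asks whether the sensations can "constitute a complementary tool for screening for obstructive sleep disorders". The group descriptions at the end of the document give sex, mean age and mean BMI for 41 cases and 60 controls, without SDs.

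**The concern.** Disease status and recruitment source cannot be allocated, so the groups in F and G are not randomised whatever the arrival-order sentence means. A reader who trusts the title would assume comparable groups; the group descriptions show that they are not.

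Age, sex and BMI are known before the examination starts and are not among the 18 scored items. If a score correlates with BMI, and cases are much heavier than controls, the score will separate the groups even if it carries nothing of its own. A significant crude ANOVA and an AUC above 0.5 are therefore compatible both with a useful score and with one that only reflects body size. The question whether the score can complement existing screening needs an analysis that tells these apart, and the text describes none.

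**Working it through.** **Counts.** 41 + 60 = 101, the size of the second file; 9 + 18 + 14 = 41; 13 + 28 = 41; 20 + 40 = 60. With normal CHR patients excluded from that file, all its cases are CHR and all its controls non-CHR. Sections F and G do not name their file; the link comes from heading B.

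**Imbalance, from the printed figures.**

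| | Cases (41) | Controls (60) | Difference |
|---|---|---|---|
| Men | 28 (68.3%) | 20 (33.3%) | 35.0 points |
| Mean BMI, kg/m² | 30.70 | 22.78 | 7.92 |
| Mean age, years | 49.30 | 41.76 | 7.54 |

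Odds ratio for male sex = (28 × 40)/(13 × 20) = 4.31. SE of log OR = √(1/28 + 1/13 + 1/20 + 1/40) = 0.433, so the 95% CI is 1.84 to 10.07. Fisher p = 0.0006. Sex alone has sensitivity 68.3%, specificity 66.7% and Youden 0.35.

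**BMI or age alone (SDs assumed).** With equal-variance normal distributions, AUC = Φ(d/√2), where d = mean difference/SD.

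- BMI SD 4, 5, 6, 7, 8: AUC 0.92, 0.87, 0.82, 0.79, 0.76.
- Age SD 8, 10, 12, 14, 16: AUC 0.75, 0.70, 0.67, 0.65, 0.63.

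The score's own accuracy is not in the text, so these are not compared with it.

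**Simulation.** 2,500 studies per setting, 41 vs 60; sex fixed at the printed counts; normal BMI and age with the printed mean differences, independent within groups; (BMI SD, age SD) = (4, 8), (6, 12), (8, 16). The SDs, the within-group correlation r between score and BMI, and the score AUC are assumptions.

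*(i) Score with no added information: proportion with p < 0.05.*

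| | SDs (4, 8) | (6, 12) | (8, 16) |
|---|---|---|---|
| Crude, r = 0.1 | 15.7% | 10.8% | 8.2% |
| Crude, r = 0.3 | 82.6% | 48.7% | 30.0% |
| Crude, r = 0.5 | 99.8% | 89.6% | 67.2% |
| ANCOVA, any of these r | 5.0% | 5.2% | 5.3% |
| Likelihood-ratio test, any of these r | 7.1% | 6.3% | 5.9% |

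A hand check of the crude column: the expected shift is r × d, for example 0.3 × 7.92/4 = 0.59 SD. The normal-theory rejection rate for that shift is 83%, in agreement with 82.6%.

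*(ii) Score independent of the covariates: proportion detected.*

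| Score AUC | ANCOVA | Likelihood-ratio test | CI for change in AUC above 0 |
|---|---|---|---|
| 0.65 | 41% to 57% | 37% to 59% | 4% to 8% |
| 0.69 | 59% to 79% | 54% to 81% | 8% to 20% |
| 0.75 | 85% to 97% | 79% to 97% | 17% to 49% |

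Ranges run from SDs (4, 8) to (8, 16). At AUC 0.69 the mean change in AUC is only 0.009 to 0.032, because the baseline AUC from age, sex and BMI is already 0.95 to 0.83. The change-in-AUC intervals used a ridge fit with bootstrap of the fitted predictions, without refitting.

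**Cost in precision.** With covariates independent within groups, R² of status on age, sex and BMI = cD²/(1 + cD²), where c = (41 × 60)/101² = 0.241 and D² is the sum of squared standardised differences. For (4, 8): D² = 3.92 + 0.89 + 0.56 = 5.36, R² = 0.564, SE inflation √(1/(1 − R²)) = 1.51. For (6, 12) and (8, 16) the inflation is 1.28 and 1.19, before any gain from explained variance.

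**BMI overlap.** Expected numbers beyond the other group's mean are n × Φ(−d). At SD 4: 1.0 of 41 cases and 1.4 of 60 controls. At SD 8: 6.6 and 9.7.

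**The case against.** Crude sensitivity and specificity are legitimate descriptions of a test and need no adjustment. The stated goal is modest: the comparison "will determine if the sensitivity of the inputs is comparable between the groups and if a tool for screening sensory inputs is possible". Unadjusted discrimination is a reasonable first step towards that, the documents name no comparator, and no sentence claims value beyond age, sex and BMI. The output of F and G is not visible, and section D could include BMI or age. Only the sex odds ratio and the two mean differences come from the documents; over r = 0.1 to 0.5 the crude rejection rate runs from 8% to nearly 100%, which says little about this particular study. The remedy is weak as well: overlap in BMI may be thin, power is moderate, a null result proves nothing, and adjustment leaves recruitment source and reference standard confounded with disease.

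Much of this stands. The crude analyses should stay, the size of the problem depends on unknown SDs and correlation, and the limits of adjustment must be stated. It does not remove the point. The design label is contradicted by the group definitions without any simulation. The aim of a complementary tool makes added information relevant even without a named comparator. A pairwise Spearman correlation, whatever its variables, is not an adjustment.

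**Conclusion.** The concern holds, in two parts of different strength.

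The randomised label is wrong as written: the contrast is between diagnosed CHR patients and non-CHR controls. This needs no assumption.

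The missing adjustment is a gap that is cheap to narrow. The groups differ on all three variables, by 35 percentage points in men, 7.92 kg/m² in BMI and 7.54 years in age, and the method text describes no analysis that would show information beyond them. Under the assumed SDs, a score that adds nothing can still give a significant crude difference in anything from 8% to nearly 100% of studies as r goes from 0.1 to 0.5, while ANCOVA holds about 5%. This does not show that the score merely reproduces age, sex and BMI; the described analyses cannot tell either way. Confidence is moderate, because the judgement rests on the method text without the output figures.

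**What to change.** **Wording.** Describe the study as a non-randomised case-control diagnostic accuracy study. Correct or clarify the arrival-order sentence, for example if it means order of examination. Name the variables correlated in section D, and the data file used in F and G.

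**Analysis.** Keep the crude ANOVA and ROC. Beside them, labelled post hoc and exploratory, report:

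- ANCOVA of IFS, and separately of the total score, on status plus age, sex and BMI.
- A logistic model of OSA on age, sex and BMI, with and without IFS. Give the adjusted odds ratio with CI from a penalised fit, naming the penalty and the interval method beforehand, and take the inference from the likelihood-ratio test for IFS.
- The change in AUC with its CI as description only, noting its low power at 41 vs 60 and that an interval including zero does not show absence of added value.
- The total score in a separate model, leaving out items 17 and 18 (2 + 1 = 3 of 26 points) or flagging that Epworth and FFF also served to define the controls.

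**Limitation to state.** Neither crude nor adjusted results separate OSA status from CHR versus non-CHR source, or from the different reference standards (subjective scales for controls; polysomnography is mentioned only for CHR patients). No claim of screening value beyond age, sex and BMI should rest on these data alone.

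**Cost.** A short addition in R on data already held: age and BMI are on the second form and sex is tabulated. The downsides are these:

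- The SE of the status effect is larger by a factor of about 1.2 to 1.5.
- If the BMI SD is near 4, ANCOVA extrapolates across thin overlap.
- The unpenalised likelihood-ratio test is slightly liberal (6% to 7%), and 41 cases for 4 terms is about 10 per term.
- A null adjusted result is inconclusive.
- BMI may lie on the pathway to OSA, so crude and adjusted results should be shown together.

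### The prediction and cut-off analyses use only composite scores (IFS, TFS), so a positive result does not show that the patient's own sensations help to screen for OSA

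*Combined protocol and SAP*

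**What the plan says.** The second study question in the protocol's introductory part reads: "Can the sensations of ventilatory flow/intraluminal pressure felt by the subject constitute a complementary tool for screening for obstructive sleep disorders".

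SAP Section C defines three nested scores:
- "Parameter ST1+ST2 (SubTotal1+ SubTotal2) = subjective sensitivity of patients"
- "Parameter ISF (Intermediate Final Score) = subjective sensitivity of patients and practitioner"
- "Parameter TFS (Total Final Score) = subjective sensitivity of patients and practitioner + valuable factors"

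Section E deals with the scores other than IFS and TFS: "To analyse any differences in sensitivity between patient groups, Kruskal-Wallis tests were applied", using the STATUS3 (healthy versus pathological) and STATUS4 classifications. Its reading rule is that "having a p-value greater than 1% and ideally greater than 5% would indicate the absence of differences between groups". It then tests each group against zero by Wilcoxon and reports rejection: "This is the case for all the patient groups tested on ST1, ST2 and ST1+ST2".

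Section F, on prediction of pathological status, applies ANOVA to IFS and TFS. Section G is headed "Determination of cut-off values for IFS and TFS" and covers sensitivity, specificity, the Youden index and ROC curves. Neither section's text names ST1, ST2 or ST1+ST2.

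**The concern.** The title and the second question are about what the subject feels. The scores carried into prediction and cut-offs contain that together with other things. IFS adds palpation of the buccal floor (item 7), audible ventilation (item 8) and a measured range of movement (item 5). TFS adds tongue posture, nasal breathing, snoring, day and night breathing route, dento-skeletal class, tonsils, Mallampati, Epworth and FFF.

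If such a composite separates patients from controls, its ROC curve does not say which part does the work. The one place where the patient score meets disease status, Section E, is set up as a check of equality and is not carried into the answer to the second question. The study could therefore report predictive value for subjective airflow sensation when the separation comes mainly from the therapist's findings or known risk factors, and no described analysis would measure the share due to sensation.

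**Working it through.** **Step 1. Reproduce the stated maxima** (18-item form, highest score per item).

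- Items 1-8: 1+1+2+2+2+2+2+1 = 13, the stated IFS maximum.
- Items 9-18: 2+1+1+1+2+1+1+1+2+1 = 13. Total 13+13 = 26, the stated final maximum.

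**Step 2. Split the points by source.**

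| Set of items | Points | Share of IFS (13) | Share of TFS (26) |
|---|---|---|---|
| Felt manoeuvres: 1-4 and 6 | 1+1+2+2+2 = 8 | 62% | 31% |
| Same plus item 5 (measured range) | 8+2 = 10 | 77% | 38% |
| Felt manoeuvres plus self-reported items 10-13 | 8+(1+1+1+2) = 13 | not applicable | 50% |
| Therapist items 7-8 | 2+1 = 3 | 23% | 12% |

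**Step 3. Can the printed thresholds be met without felt points?**

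- TFS ≥ 11: the other items give up to 26-8 = 18, so yes. If item 5 is grouped with the patient items, the others still give 26-10 = 16.
- IFS ≥ 8: the other items give at most 13-8 = 5, so at least 8-5 = 3 felt points are needed. With item 5 grouped with the patient items, the figures are 3 and 5.

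**Step 4. What Section E tests.** With two groups, the Kruskal-Wallis test is the Mann-Whitney test, and AUC = U/(n1 × n0). On made-up data for 41 versus 60, both gave p = 0.743. By STATUS3, Section E is therefore in effect a test of AUC = 0.5. It gives neither the AUC nor its interval, and a large p-value does not establish equality. The Wilcoxon tests against zero do not bear on discrimination: every group can lie above zero without the groups differing.

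**Step 5. What the sample could show.** The SAP gives no alpha or power for this. Assuming two-sided 5% and 80% power, with 41 OSA patients and 60 controls, the Noether approximation gives:

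detectable AUC = 0.5 + (1.960 + 0.842)/√(12 × 41 × 60/101) = 0.5 + 2.802/17.10 = 0.664.

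An AUC of about 0.66 for the felt items is within reach, and a confidence interval would be informative.

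**Step 6. Illustration only.** The documents give no item frequencies, so every rate here is assumed. Patient items and item 5 were given the same distribution in both groups (patient-item AUC 0.50), and only items 7-8 differed; 1,000 samples of 41 versus 60 were drawn per row.

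| Items 7-8 positive, controls vs OSA | IFS AUC | ANOVA p < 0.05 |
|---|---|---|
| 30% vs 50% | 0.58 | 29% |
| 20% vs 60% | 0.66 | 80% |
| 20% vs 80% | 0.74 | 99% |

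This shows that the mechanism is possible. It does not estimate its size in this study.

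**The case against.** The strongest reply has four parts.

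1. **The patient score is compared with disease status.** A reader might infer that ST1+ST2 is never tested against OSA. The text does not support that: Section E compares the scores other than IFS and TFS by STATUS3, which is in effect a discrimination test. What remains is the lack of an AUC, cut-off or increment, and the reading of a large p-value as equality.

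2. **The question says complementary.** A composite that contains sensations is not irrelevant, the SAP openly labels IFS as patient plus practitioner, and IFS ≥ 8 cannot be reached without felt points. This stands. But a complementary tool has to add something to the other information, and needing some felt points is not evidence that those points differ between groups.

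3. **The source of ST1 and ST2 is not stated.** Section C lists them beside IFS, which suggests items 1-6 of the 18-item form. Section E treats zero as no sensitivity, which fits the on/off 7-item form better, since items 3 and 4 of the longer form also score 0 when the effect is felt late in the movement. If the 7-item form is meant, the plan may be coherent: everyone can feel the manoeuvres, while how early they feel them may discriminate. If the 18-item form is meant, ST1+ST2 includes item 5, which is not a sensation. Either way, no patient-only ROC analysis is described.

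4. **The 31% share depends on classification.** Items 10-13 are labelled subjective perception on the form; counting them gives 50%. Both figures belong in the report.

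A reader might also infer that a non-significant Section E result would prove that any IFS or TFS discrimination comes from the other items. It would not: non-significance is not equality, and the two sections may use different forms.

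**Conclusion.** The concern holds in a limited form. As described, Sections F and G can show that a composite clinical score separates the groups; they cannot show that patient sensation contributes to that separation. Felt-manoeuvre items supply 8 of 13 IFS points and 8 of 26 TFS points (13 of 26 on the wider definition). The gap is greatest for TFS, whose threshold can be met with no felt-manoeuvre points at all.

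The documents do not show that sensation lacks predictive value. The conclusion rests on the text of Sections C to G and the scoring on the 18-item form. The figures for Sections E to G are not visible, and the variables correlated in Section D are not named. Severity is should-fix: the data can probably answer the question, but the described analysis does not.

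**What to change.** - State which form, and which items, ST1 and ST2 come from.
- In Sections F and G, in the 101 patients of file 2, add for the felt items alone (1-4 and 6) the AUC with 95% confidence interval, sensitivity, specificity and Youden index. Repeat with item 5 included as a sensitivity analysis.
- On the same patients, report paired AUC differences from felt items to IFS and from IFS to TFS. Also report the increment of the felt items over the practitioner and risk-factor items, for example TFS (26 points) against TFS without the felt items (18 points). These are fixed sums, so no model fitting is needed.
- In Section E, replace the reading of a large p-value as absence of difference with an estimate and its interval.
- Attribute predictive value to subjective feeling only if the felt items discriminate or add value; otherwise describe IFS and TFS as composite clinical scores.

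Cost: SAP wording and a few further ROC calculations on items the 18-item form already records, assuming item-level values are held in file 2 or can be taken from the forms. The downside is that the headline claim may become less favourable.
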